3.1 Quality Assurance

Standardised protocols have been developed for NIR laser light treatment, refraction, fluorescein angiography, microperimetry, measurement of best-corrected visual acuity, OCT measured subfield volume and thickness.

The major quality assurance features of the study are:

- Standardised eligibility and exclusion criteria
- Adherence to treatment protocol and follow-up schedule
- Trained BCVA and imaging technicians
- Monthly meetings of personnel to review methods and discuss problems

3.2 Organisational Structure of the Study Group

The centre will have trained BCVA examiners, a study coordinator, a photographer, an ophthalmologist performing the NIR laser light delivery, and an optical coherence tomography (OCT) examiner. There will be no masking in this study.

4 Participant Eligibility

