Patients with diabetic macular oedema in one eye as defined by the eligibility criteria will receive thrice weekly 90 second treatments with NIR laser, supplied by Ellex, for 4 weeks. Twenty one patients will be sequentially allocated into three groups to receive laser doses 25, 100 or 200 mW/cm². The central 1 mm will be shielded so that the fovea will be protected in the event of any unanticipated toxic effect on the retina.

1.3.1 Primary outcome:

- Reduction in central macular thickness measured by optical coherence tomography at the conclusion of treatment and at 8 weeks compared with baseline.

1.3.2 Secondary outcomes:

- LogMAR Best Corrected Visual Acuity (BCVA)
- Time to oedema reduction
- Time to oedema recurrence
- FFA assessment of leak and capillary closure before (at baseline) and after intervention (week 5 and 16)
- Change in retinal sensitivity (dB) as measured by microperimetry from Baseline to Week 1, Week 5, Week 16 and 6 month follow up visit.

1.4 Power calculation:

This study is an exploratory study designed to provide estimates of outcomes for future studies, therefore power calculations have not been applied. Seven patients per group will be sufficient to produce these estimates and will give an indication of the effective dose range

1.5 Significance:

This study will shed light on whether a novel treatment that may complement existing treatments is safe and whether it warrants further investigation in a larger study

2 Research Plan

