2.2.2 Secondary Outcome measures at 1month, 8 weeks, 12 weeks and 16 weeks

- Best corrected LogMAR Visual Acuity (VA)
- Time to oedema reduction
- Time to oedema recurrence
- FFA assessment of leak and area of ischemia before and after intervention
- Change in retinal sensitivity (dB) as measured by microperimetry from Baseline to Week 5, 8, Week 16 and 6 month visit.

2.2.3 Safety outcomes will be:

- Any loss of VA
- Any increase in macular thickness as measured by OCT

3 Design

A cohort of 21 patients satisfying the inclusion criteria will be recruited from the outpatient hospital clinic. They will be sequentially allocated into one of three groups. Each group will have seven patients with group 1 enrolment completed first, followed by group 2 and finally, group 3. Each group will be managed identically but will receive a different dose of NIR energy.

Group 1 will be treated with a dose of 25 mW/cm² for 90 seconds (now fully enrolled)

Group 2 will be treated with a dose of 100 mW/cm² for 90 seconds (now fully enrolled)

Group 3 will be treated with a dose of 200 mW/cm² for 90 seconds.

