8.1 Primary and Secondary Outcomes

Primary outcome:

- Reduction in high definition Spectral Domain Heidelberg Optical Coherence Tomography (OCT) subfield volume measurements at 8 weeks.

Secondary outcomes at 1 and 2 months:

- LogMAR VA
- Time to fluid reduction
- Time to oedema recurrence
- FFA assessment of leak and capillary closure before (at baseline) and after intervention (Week 5 and 16)
- Change in retinal sensitivity (dB) as measured by microperimetry from Baseline to week 1, week 5, week 8 and Week 16

Safety outcomes will be:

- Any loss of BCVA/VA
- Any increase in any OCT subfield

9 Statistical aspects of the study, safety and reporting

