9.2 Statistical Analysis of OCT measurements

Retinal thickness measurements will be checked for artefacts. Only scans where the software was able to pick up the retinal thickness between the internal limiting membrane and the retinal pigment epithelium will be used.

The principal measurement of macular thickness will be the reading that appears in the central circle. Absolute change and percentage change in “abnormal thickness” will also be analysed in each subfield.

OCT measurements will be made and entered into the database.

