12.1 Fundus Photography

Fundus camera photography for FFAs and colour photographs are to be performed digitally. All digital images will be de-identified for grading.

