12.3 Fluorescein Angiography

Fluorescein injection: 5ml of 10% sodium fluorescein will be rapidly injected into the antecubital vein. Other injection sites may be substituted if necessary.

Standard angiogram will be presented as 4 UP (RF, <30sec, 60-90 sec, 5 min) at baseline, Week 5 and week 16 or early exit visits.

13 Optical Coherence Tomography & Fundus Autofluorescence

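### The blanket no-masking rule makes no exception for image graders, so the fluorescein angiography outcome can be read with visit and dose group known

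*Protocol*

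**What the plan says.** Section 3.2 lists the centre's staff (visual acuity examiners, coordinator, photographer, treating ophthalmologist, OCT examiner) and ends: "There will be no masking in this study". No role or task is excepted.

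Section 12.1 covers FFA and colour photography: "Fundus camera photography for FFAs and colour photographs are to be performed digitally", followed by "All digital images will be de-identified for grading". Section 13, on OCT and autofluorescence, has no matching sentence.

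Section 8.1 names as a secondary outcome "FFA assessment of leak and capillary closure before (at baseline) and after intervention (Week 5 and 16"). Section 1.3.2 names the same outcome, and Section 2.2.2 gives it as leak and area of ischaemia. Section 12.3 schedules the angiograms "at baseline, Week 5 and week 16 or early exit visits".

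For OCT, Section 9.2 says "Retinal thickness measurements will be checked for artefacts", and keeps only scans on which the software could measure retinal thickness.

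On allocation, Section 3 says: "Each group will have seven patients with group 1 enrolment completed first, followed by group 2 and finally, group 3". It adds that groups 1 and 2 are already fully enrolled.

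**The concern.** Giving treatment openly does not require reading the images openly. With sequential dose cohorts, masking the treatment would be hard. Keeping a grader unaware of visit and dose is a separate matter, and Section 3.2 rules it out along with everything else.

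The trial has no untreated control and no randomisation. Its evidence is the change from baseline within patients and the pattern across three doses. A grader who knows which angiogram is post-treatment can influence the first; one who knows the dose can influence the second. An expectation already exists, because Section 2.1 reports that the first cohort's results may point to a delayed benefit after treatment ends. Section 1.4 says the trial is meant to supply estimates for later studies and an indication of the effective dose range. Reader bias would carry straight into both.

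**Working it through.** The protocol gives no figure to reproduce. Section 1.4 says "therefore power calculations have not been applied", and no effect size or alpha is set for these outcomes. The check compares sections and counts images.

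**1. Does the rule reach the graders?** Section 3.2 is unqualified. Section 12.1 shows that grading is a planned step. No section says graders are kept unaware of visit or dose group. As written, the rule covers them.

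**2. Does de-identification mask them?** No. It removes who the patient is. No section says that it removes visit label, date or dose group. Groups enrol one after another, so an acquisition date can place an image in its dose group even if the dose is not shown.

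**3. Which outcomes depend on a reader?**

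| Outcome | How it is obtained | Exposure |
|---|---|---|
| FFA leak, capillary closure or ischaemia (secondary) | Graded images; no automated measurement described | Direct |
| OCT thickness or volume (primary) | Software reading, then a check for artefacts | Only through which scans are kept |
| Colour photographs | Covered by Section 12.1, tied to no listed outcome | Indirect |

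**4. How many images?**
- Patients: 3 groups × 7 = 21, which agrees with the stated total.
- FFA sets: 21 × 3 (baseline, Week 5, Week 16) = 63.
- Colour sets: 21 × 4 (baseline, Week 5, Week 16, 6 months; Section 12.2) = 84.
- FFA sets from groups 1 and 2: 14 × 3 = 42.
- Colour sets from groups 1 and 2: 14 × 4 = 56.

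These are planned maxima; early exits would change them.

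**5. Does the state of enrolment affect the remedy?** Yes. If masked grading applied only to images still to come, groups 1 and 2 could be read openly and group 3 masked. Grading method would then be confounded with dose. The documents do not say whether any group 1 or 2 images have been graded, so the procedure has to cover all three cohorts.

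**6. Would batch grading interfere with the visits?** The discontinuation rule in Section 6.4 uses OCT thickness and letters lost, not FFA grades. Graded FFA can therefore wait for a batch. OCT has to be read at the visit for that rule, so recoded OCT decisions for the analysis must be a second, separate step.

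**The case against.** The strongest reply is that this is a declared open, exploratory study and that its primary outcome is a software measurement. The no-masking sentence closes a list that names no image grader, so applying it to grading is an inference. Section 3.1 refers to standardised protocols for angiography and OCT that are not shown and may set out reading procedures. Part of the FFA outcome, the area of ischaemia, might be a measurement rather than a judgement.

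Some of this stands. The exposure falls mainly on one secondary outcome. The unseen procedures might already keep graders unaware, but they would then contradict the protocol's flat statement, which would still need correcting. Outlining an area of ischaemia would still depend on a reader unless it is automated, and no automation is described.

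A reader might also infer more than the documents support:

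- That the images are already masked in all but name. De-identification is not masking, and it is stated only for FFA and colour images.
- That Sections 3.2 and 12.1 contradict each other. They do not: images can be de-identified and still be graded openly.
- That the primary outcome is compromised. Only the artefact check and scan exclusion involve a person's judgement.
- That the bias can be put at a number. The documents contain nothing from which to derive one.
- That masked grading would cost nothing. The documents do not address cost, and re-reading earlier cohorts is real work.

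**Conclusion.** The concern holds for image grading. The protocol states a rule that leaves the FFA secondary outcome open to bias from knowledge of visit and dose, in a trial whose comparisons are before against after and one sequential dose group against another. It should be changed, because the exposure is avoidable with little extra effort at a step that already exists.

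The size of any bias is unknown. What can be stated is its reach: up to 63 FFA sets in 21 patients and, to a lesser degree, the choice of OCT scans that enter the primary analysis. The conclusion assumes that FFA grading involves human judgement and that no unseen procedure already conceals visit and dose. Masked reading would remove this one source of bias; it would not make up for the lack of a concurrent control.

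**What to change.** 1. **Section 3.2:** limit the sentence to say that participants and treating staff are not masked.
2. **Section 12.1:** add that, at de-identification, visit label, acquisition date and dose group are removed and replaced by a neutral code. FFA and colour images from all three cohorts are then graded in random order across visits and groups, under one procedure, by an existing reader unaware of visit and dose.
3. **Groups 1 and 2:** re-read under that procedure any images already graded openly, so that grading method does not differ by dose.
4. **Section 9.2:** make artefact and exclusion decisions for the analysis on recoded OCT scans, separately from the OCT reading used during visits, which is unaffected.

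**Cost:** recoding and shuffling at an existing step, grading in batches, and re-reading up to 42 FFA sets (and up to 56 colour sets, if those have been graded). No new patient procedure is needed. No extra staff are needed if someone already on the team can read without knowing visit and dose; the documents do not show whether such a reader is available.

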4.1 Patient Consent

The study requires that written informed consent is obtained from each participant prior to their enrolment in the study. The participant will be asked to sign the consent form only after an investigator has explained the purpose of the study and the participant has had time to read and understand the information sheet.

With the consent of the participant, it is the Investigator's responsibility to notify the primary care physician of the participant's participation in the study, provided that such a physician can be identified for the participant. A letter will be sent to the physician stating the nature of the study. A copy shall be retained by the study site.

4.2 Eligibility of Participants into the Study

4.2.1 Inclusion Criteria

- a) Diabetic Macular Oedema with centre involving thickness of $>300\mu\text{m}$
- b) Age ≥ 18 years
- c) Diagnosis of diabetes mellitus
- d) Best corrected visual acuity of 6/9 to 6/60 (letters 77- 33)
- e) Intraocular pressure 6 to 25 mmHg
- f) Written informed consent has been obtained.

4.2.2 Exclusion Criteria

- a) Known allergy to agents used in the study e.g. fluorescein
- b) Women who are pregnant, nursing, or planning a pregnancy, or who are of childbearing potential and not using reliable means of contraception. A woman is considered of childbearing potential unless she is postmenopausal and without menses for 12 months or is surgically sterilised
- c) Loss of vision due to other causes (e.g. age related macular degeneration, myopic macular degeneration, retinal vein occlusion)
- d) Macular oedema due to other causes
- e) An ocular condition that would prevent visual acuity improvement despite resolution of oedema (such as foveal atrophy or substantial premacular fibrosis)
- f) Treatment with intravitreal triamcinolone acetonide (IVTA) within the last 6 months or peribulbar triamcinolone within the last 3 months, or anti vascular endothelial growth factor (VEGF) drugs: ranibizumab and aflibercept, within the last 2 months.
- g) Cataract surgery within the last 3 months
- h) Retinal laser treatment within the last 4 months
- i) Media opacity including cataract that already precludes adequate macular photography or cataract that is likely to require surgery within 6 months

- j) Intercurrent severe disease such as septicaemia, any condition which would affect follow-up or photographic documentation (e.g. geographical, psycho-social)
- k) History of chronic renal failure requiring dialysis or renal transplant
- l) Blood pressure >180/100
- m) Patient has a condition or is in a situation that in the investigator's opinion may put the patient at significant risk, may confound the study results, or may interfere significantly with the patient's participation in the study

4.3 Bilateral/Fellow Eye Enrolment

If both participants' eyes are eligible for the study, only the eye with the worse DMO will be enrolled.

5 Entry into the Study

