2.2 Objective

This will be a 1 month exploratory study, with outcome measures assessments at 8 weeks and further assessment visit as 12 and 16 weeks, followed by a 6 month safety visit.

The specific aim of the study is to test the following hypothesis:

- That treatment with NIR light reduces diabetic macular oedema

Outcomes

Variables related to the progression or resolution of diabetic macular oedema will be serially examined in the study eye of all patients to determine the effects of NIR treatment. These are:

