5.2 Baseline Examination (Screening Visit)

If the patient is willing and has agreed to participate in the study then a complete baseline examination is conducted (does not need to be the same day as the signing of the consent) which includes the following

- a) Visual Acuity. Best corrected visual acuity will be assessed on LogMAR chart
- b) Intraocular Pressure (IOP) measurement
- c) Slit lamp examination for grading of lens opacities
SD OCT: High definition Spectral domain Volume Scan or Macula Cube
Cross Hair scan or HD 5-line raster
- d) Fundus photography and fluorescein angiography. See Section 12 for photography and angiography details.
- e) Fundus autofluorescence. See Section 13.1
- f) Urine pregnancy test (for women of child bearing potential only)
- g) Blood pressure
- h) Assessment of concomitant medications and medical history
- i) Visual function as assessed by Microperimetry

Full baseline assessment will be performed on the Tuesday or Friday on the week immediately prior to starting NIR treatment. If clinics/staff are not available for baseline assessment on Tuesday or Friday, another day in the week immediately prior to starting NIR treatment may be selected, however the remaining treatment and visit schedule must be adhered to according to the protocol.

5.3 Day 1

Once the patient has met all of the eligibility criteria they will return for the Day 1 visit which will occur on the Wednesday the week after screening. The following procedures will occur at this visit:

- a) AE and Conmed history
- b) Microperimetry
- c) Dilation of study eye
- d) Confirmation of eligibility
- e) NIR light treatment

6 NIR Light Treatment

NIR light treatment will commence on the Wednesday of the next week after the baseline visit.

The procedure will be performed whilst the participant is seated at a slit lamp according to the set protocol:

The patient will be seated at the slit lamp laser delivery system and after the eye has been dilated and anaesthetised with topical eye drops a standard fundus contact lens (area centralis) will be placed on the eye through which the posterior pole will be visualised while the treatment is delivered.

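### The qualifying scan is also the only scheduled pre-laser OCT and every patient is treated, so a fall from it cannot by itself show a NIR effect

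*Protocol*

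**What the plan says.** - **Aim.** Section 2.2 sets out to test a hypothesis: "That treatment with NIR light reduces diabetic macular oedema".
- **Primary outcome.** Section 1.3.1: "Reduction in central macular thickness measured by optical coherence tomography at the conclusion of treatment and at 8 weeks compared with baseline". Sections 2.2.1 and 8.1 word the measure differently (adding or substituting volume), but it remains a reduction on OCT.
- **Entry.** Section 4.2.1a requires "Diabetic Macular Oedema with centre involving thickness of" more than 300 microns. Section 4.3 adds: "If both participants' eyes are eligible for the study, only the eye with the worse DMO will be enrolled".
- **Reference scan.** Section 5.2 makes the screening visit the baseline examination and includes the SD-OCT. Section 15 has a single combined screening/baseline column.
- **Day 1.** Section 5.3: "Once the patient has met all of the eligibility criteria they will return for the Day 1 visit". The Day 1 list has microperimetry, dilation, confirmation of eligibility and laser, but no OCT. The next OCT is on Friday of Week 1, two days after treatment 1 and, by note c of Section 15, before treatment 2.
- **No untreated group.** Section 1.3: "Twenty one patients will be sequentially allocated into three groups to receive laser doses 25, 100 or 200 mW/cm²". Section 3: "Each group will be managed identically but will receive a different dose of NIR energy".

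**The concern.** An eye admitted because its reading is high will on average read lower at the next visit, because part of the high reading is chance fluctuation. If the reading that admits the eye is also the value from which the reduction is counted, that drop enters the primary outcome. A concurrent untreated group would show the same drop and let it be subtracted, but here the only reference is zero change. The shift is common to all three doses. It therefore affects the before-after reading more than the contrast between doses, which is itself sequential and not randomised.

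Two uses of the result are at stake: the test of the hypothesis in Section 2.2, and the estimates that Section 1.4 says are meant for planning future studies. An inflated reduction would carry into both.

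**Working it through.** **The plan's own figures.** Three groups of seven give 21, as stated. Section 1.4 gives no power calculation, and the protocol gives no SD, correlation, alpha or expected change, so everything below rests on assumed inputs.

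**Assumptions.** True thickness between eyes: SD 80 microns, clinic mean 330 or 380, correlation between a patient's two eyes 0.5. Within-eye visit-to-visit SD (w): 20, 30 or 40, independent between visits. No NIR effect and no natural change.

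**Threshold alone, by formula.** Let s = √(80² + w²) and a = (300 − mean)/s. Then

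expected fall = (w²/s) × φ(a)/(1 − Φ(a)).

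- Mean 380, w = 20: s = 82.46, a = −0.970, fall = 4.85 × 0.299 = 1.45 microns.
- Mean 330, w = 30: s = 85.44, a = −0.351, fall = 10.53 × 0.589 = 6.20 microns.
- Mean 330, w = 40: s = 89.44, a = −0.335, fall = 17.89 × 0.597 = 10.69 microns.

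**Three selection routes, by simulation** (1.5 million two-eyed patients per setting, no NIR effect, split into samples of 21). Each cell gives w = 20 / 30 / 40. The last column applies a one-sided 2.5% paired t test on 21 patients. That test is an assumption, because the protocol states none.

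| Route | Clinic mean | Fall (microns) | Pooled mean falls (%) | Test rejects (%) |
|---|---|---|---|---|
| Threshold alone | 330 | 2.8 / 6.1 / 10.7 | 68 / 75 / 81 | 6.4 / 9.3 / 13.4 |
| Threshold alone | 380 | 1.5 / 3.3 / 5.9 | 59 / 64 / 69 | 4.1 / 5.4 / 6.8 |
| Threshold, and thicker eye picked on the same scan | 330 | 5.0 / 10.5 / 17.6 | 80 / 88 / 93 | 12.0 / 19.7 / 29.0 |
| Threshold, and thicker eye picked on the same scan | 380 | 4.2 / 8.9 / 14.9 | 76 / 84 / 89 | 9.5 / 15.4 / 22.2 |
| Eye qualified and picked on an earlier scan, above 300 confirmed at baseline | 330 | 1.3 / 3.2 / 6.2 | 59 / 64 / 70 | 3.9 / 5.1 / 7.1 |
| Eye qualified and picked on an earlier scan, above 300 confirmed at baseline | 380 | 0.6 / 1.6 / 3.2 | 54 / 57 / 60 | 3.0 / 3.5 / 4.5 |

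Without selection the last two columns would be 50% and 2.5%.

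**Smaller fluctuation.** At w = 10 the fall is 0.4-0.7 microns from the threshold alone and 1.1-1.3 with the thicker eye picked on the same scan.

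**Reference scan not used for selection.** The expected change is about 0 and the test rejects in 2.3-2.7% of trials, given independent fluctuation between scans.

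**Wider inputs.** With mean 300-450, SD 80-120 and a baseline to week 8 correlation of 0.70-0.95, threshold plus worse eye gives a fall of 3-39 microns. In the middle case (mean 400, SD 100, correlation 0.80) it is 16 microns, and an untreated worsening of about 16 microns by week 8 would cancel it.

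**The case against.** **The shared scan is inferred.** Section 5.1 has patients examined for eligibility at an initial visit, before the baseline examination, so eyes may have been chosen on an earlier clinic scan. This stands as a limit on size. However, no OCT is named or required at that visit, so the protocol does not ensure separation. Some shift also remains in that case, because the threshold still applies at baseline.

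**The worse-eye rule reaches only some patients.** It applies when both eyes qualify, and worse oedema is not defined as greater thickness. This also stands. The threshold is the part that acts on every patient, and the worse-eye rows are an upper scenario.

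**The study is exploratory and states no test.** It is true that the protocol fixes no paired test, alpha or claim limit, and inference may sit in an analysis plan that is not shown. The rejection rates are therefore conditional on such a test being used. But Section 2.2 does speak of testing a hypothesis, and an exploratory label does not remove bias from an estimate.

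**The effect hoped for is larger.** The pilot study cited in Section 2.1 reports a 20% mean reduction, in non-centre-involving oedema. At 300 microns that is 0.20 × 300 = 60 microns, beyond every figure above. A fall of that size could not be put down to selection under these inputs, but a modest one could.

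**Stronger readings that a reader might infer.** One is that a reduction is the expected result whatever the disease does, or that all error points toward benefit. Both require stable disease without treatment, which the protocol does not establish. Another is that at least one of the three doses will almost always show a mean reduction. That happens in 1 − 0.5³ = 87.5% of trials with no selection at all, so it says little.

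**Conclusion.** The point holds as a limit on interpretation. Selection on thickness, a single scheduled pre-laser scan and the absence of an untreated arm mean that part of a mean fall may be regression to the mean. A fall from that scan therefore does not by itself support the hypothesis in Section 2.2.

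The size is unknown from the protocol. Under the assumed inputs (within-eye SD 20-40 microns, stable disease) it is about 1.5-11 microns from the threshold alone, at most about 4-18 with every eye picked by thickness on the same scan, and 0.6-6 if eyes were qualified and picked earlier. For the first two routes a pooled mean reduction appears in about 60-93% of trials without any effect, and the assumed t test would reject in about 4-29%. For the third the figures are 54-70% and 3-7%. The documents do not support taking the upper end as the likely value, or concluding that a positive result is near certain with an inert treatment.

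**What to change.** 1. **Section 2.2.** Replace the statement that the study tests its hypothesis with the aim of estimating the change from baseline by dose. State that a reduction from the qualifying scan is not by itself evidence of a NIR effect. Cost: wording only.
2. **All 21 patients, no new data.** Add a supporting analysis of change to week 5 and week 8 from the Week 1 Friday OCT, which precedes treatment 2 and is not used for selection. It omits any effect of treatment 1, and it removes the artefact fully only if fluctuation at that scan is independent of fluctuation at screening.
3. **Optional, for Group 3 patients still to be enrolled.** Add a pre-laser OCT on Day 1, when the study eye is already dilated, as a supporting reference. Keep the screening scan as the common reference across doses. Cost: one short scan in at most seven patients, since Groups 1 and 2 are fully enrolled.

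A claim limit calibrated from the Week 5 Monday and Tuesday scans would not serve. Expected regression also depends on the mean and SD of unselected eyes and on the between-eye correlation, which the trial does not record. One-day variation is only a lower bound on the fluctuation that matters, so such a limit would be too lenient.
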